- 2) Previous studies which tested if BCG can detect sleep disturbances are encouraging, despite using remote techniques: Da Woon et al. used an unobtrusive polyvinylidene fluoride film sensor on a bed mattress to record BCG signals in a selected group of 10 OSA patients and 10 controls (52, 53). They calculated heart rate (HR) and heart rate variability (HRV) from J-J BCG interval and detected awakening periods in OSA patients with an accuracy of 97%. *The authors could however not determine why sleep was fragmented with this technique.* Zaho et al. also used a micro-movement sensitive bed mattress in subjects with a BMI < 35 kg/m² and no other concomitant cardiorespiratory disease (54). HRV was also retrieved from J-J BCG interval. However, *only selected periods of sleep were analysed for sleep-breathing events, a surrogate marker for obstructive, but not central apnoea.* Detection of these events was nevertheless achieved with a sensitivity of 98%, a specificity of 94%, and an accuracy of 98% (55). Last, Dehkordi et al. showed that it was possible to distinguish between central and obstructive events by recording acceleration from the suprasternal notch, the thorax and the abdomen (56). The subjects investigated were however *only normal volunteers* who performed several voluntary breaths hold in the presence of an oral nasal flow detector.

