- 3) The unique expertise of our research team is that we are capable to record SCG and BCG signals in 3 dimensions (57, 58), both linearly and rotationally (16-18). While the above mentioned studies (52-56) assessed BCG changes only in a horizontal plane (x and y axis), which is not representative of the complex cardiac mechanic, we are capable to record these changes in a third anteroposterior dimensions (z axis). This is important because of the anterior-posterior direction of the aortic arch. In addition, as emphasized in the introduction of this research proposal, an important component of the body reaction to the heart movements is rotational, which we are capable to record in 3 dimensions. Overall the combined SCG and BCG 3D-linear and 3D-rotational signals represent 6 degrees of freedom (DOF) while past BCG had only 2-DOF. For simplicity, this 6 DOF signal combination will be designated as Kino-cardiography (KCG) recordings in this research proposal. We anticipate that the unique KCG properties will considerably increase our detection capability of obstructive and central apnoea, as compared to previous studies.

2. Aims and hypothesis tested

The main hypothesis tested in our study is that KCG provides sensitive and accurate measures of obstructive and central apnoea as compared to state-of-the-art polysomnography. Our secondary hypotheses are related to modifications in the SCG and BCG parameters during the apnoea and the effects of nCPAP therapy: we believe that the KCG signals are profoundly affected by the apnoea and they are reversed to the normal baseline with the CPAP. These hypotheses will be tested through a series of studies in normal volunteers and patients.

1-MAIN HYPOTHESES:

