Group A. After a fine tuning period of the KCG signal post processing to maximise the sensitivity and specificity of voluntary apnoea detection in health subjects, we will start the first validation study. In 46 healthy volunteers, a computer program will generate random instructions of periods of normal breathing, voluntary end-expiratory breathing cessations periods (as surrogate of central apnoea) and Muller's manoeuvre (as surrogate of obstructive apnoea). Meanwhile, the KCG will record the above-mentioned parameters. The number and duration of voluntary central and obstructive apnoea will be assessed in the KCG recordings, not knowing how many were actually generated by the computer program. We will also record the ECG, heart rate, beat to beat non-invasive blood pressure (Finometer), humeral blood pressure (Dinamap), ventilation, end-tidal CO₂ (AD instruments), O₂ saturation (Nellcor), cardiac output (CO) (Philips).

Group B. In patients suspected of sleep apnoea and admitted to the sleep unit of the Erasme hospital to perform sleep test as required by their medical condition, we will simultaneously record KCG and PSG and qualitatively compare the data. Bland-Altman plots will analyse the agreement between the sleep recordings obtained with the two methods. Peculiar attention will be paid to the accuracy of the detection of obstructive *versus* central *versus* mixed apnoea, of awakenings, and of the time spend in bed. In this second phase of the study, we plan to record these parameters only in selected patients, who will not disclose marked abnormalities which could hamper the reliability of the KCG recordings, namely moderate or severe valvular disease, permanent atrial fibrillation or frequent premature contractions, atrio-ventricular conduction disturbances, medications which reduce heart rate and heart rate variability (beta blockers, anti-arrhythmic drugs, calcium blockers, ...), cardiac rhythm driven by a pace maker, heart failure of any origin, neurological diseases responsible for abnormal movements (restless leg syndrome, Parkinson disease, ataxia ...).

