Group C. In patients with a diagnosis of OSA, we will determine if KCG is capable to reliably assess the efficacy of the nCPAP therapy in comparison to simultaneous PSG recording. Ongoing adjustment in CPAP therapy pressure during the night, and its effect on cardiovascular haemodynamic assessed by the KCG, will be taken into account as well. The capability of the technique to detect changes in sleep quality will be tested both *within* subjects (before vs. after nCPAP therapy in the same patient) as well *among* the subjects investigated. The same restriction in the recruitment of the subjects of group B will be applied for the present group.

Group D. After validation of the three previous steps, we plan to extend the recordings on 100 unselected consecutive patients who will undergo PSG recordings because of complains of sleep apnoea. This will validate the clinical usefulness of KCG recording for the detection of sleep apnoea even in patients with multiples co-morbidities.

2-SECONDARY HYPOTHESES

We will test the hypothesis that the apnoeic events profoundly affected the KCG signals (PEP, LVET and PEP/LVET ratios). These parameters are affected by changes in cardiac pre- and after- load and sympathetic activity on myocardial contractility. Similarly, we plan to test the hypothesis that the isovolumic relaxation time (IVRT), an index of diastolic performance during the cardiac cycle, will be altered during the obstructive apneas, because marked variation in intrathoracic pressure result in large increases in LV transmural gradient and thereby reduce LV compliance. CPAP therapy should markedly reduce the nighttime variability in these parameters.

We will also asses the R-J interval which is related to blood pressure and determine if this parameter rises during the apneas and arousals when sympathetic activity is increased. Determination of the J-J intervals and the corresponding HRV, which is under strong autonomic control, should also present distinct changes in OSA patients, as compared to subjects receiving efficacious nCPAP therapy.

Last, breathing effort variations will be assessed. This refers to the mechanical interaction between respiration and KCG signals when sleep apnea occurs, independently from an autonomic nervous modulation of heart rate variability: when the obstructive apneic event occurs, the airflow decreases, which result in a

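### Group B's stated methods (qualitative comparison and Bland-Altman plots) estimate neither the sensitivity of KCG nor its accuracy by apnoea type, which are what the study sets out to show

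*Protocol*

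**What the plan says.** Section 2 (Aims and hypothesis tested) gives the main hypothesis for the series of studies: "KCG provides sensitive and accurate measures of obstructive and central apnoea as compared to state-of-the-art polysomnography".

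Under the main hypotheses, Group B is the first group in which KCG is recorded alongside PSG. The text states two methods, in consecutive sentences: the team will "simultaneously record KCG and PSG and qualitatively compare the data. Bland-Altman plots will analyse the agreement between the sleep recordings" from the two systems. The quantity to be plotted is not named. The next sentence sets the focus: "Peculiar attention will be paid to the accuracy of the detection of obstructive *versus* central *versus* mixed apnoea, of awakenings", and time in bed as well. No measure is attached to it.

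Section 3 (Methods) adds no analysis for Group B and leaves its sample size to be worked out from Group A. For this study's own device, sensitivity and specificity are mentioned only for the tuning phase on voluntary apnoea in healthy subjects.

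The background reports an earlier bed-sensor study in these terms: "Detection of these events was nevertheless achieved with a sensitivity of 98%, a specificity of 94%, and an accuracy of 98" per cent. Section 2 then follows an argument that KCG should detect apnoea considerably better than earlier studies did.

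The Group D text begins: "After validation of the three previous steps, we plan to extend the recordings on 100 unselected consecutive patients".

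**The concern.** The question is about detection and classification of individual events. Of the events PSG scores, how many does KCG find, how many does it invent, and does it give them the right type? Bland-Altman analysis describes the difference between two numerical measurements on the same patient. On the natural reading, the measurement is a nightly event count or rate. A count carries no information on whether the events counted by KCG are the ones counted by PSG, so misses and false detections can cancel, and so can swapped type labels. A qualitative comparison produces no estimate.

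Two things are at stake. Group B would give no figure to set against the earlier sensitivity, specificity and accuracy that the protocol itself quotes. And Group B is one of the three steps whose validation must precede Group D, yet its stated methods cannot show whether the main hypothesis holds.

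**Working it through.** **No Group B figure to reproduce.** The protocol gives no expected sensitivity, event rate, sample size or precision for Group B. Its one calculated sample size belongs to Study A: 2 × (1.96 + 1.64)² × 0.1247² / 0.09319² = 46.4, stated as 46. It does not bear on this point. Every rate below is therefore an assumption, used to test whether bias and limits of agreement determine sensitivity, PPV or type accuracy.

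**One night.** PSG scores 200 events. KCG finds 140 and marks 60 false ones, so it counts 200. Difference = 200 − 200 = 0. Sensitivity = 140/200 = 70%; PPV = 140/200 = 70%.

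**Many nights.** Assume 7 h of recording and an event rate A that is lognormal with median 20/h and log-SD 0.8.
- Mean of A = 20 × exp(0.8²/2) = 27.5/h. Variance of A = 27.54² × (exp(0.64) − 1) = 680.
- PSG count n is Poisson with mean 7A, so E(n) = 192.8.
- KCG minus PSG = false events (FP) minus missed events (FN). Limits are bias ± 1.96 × SD / 7.

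Variance of FP − FN in the main cases:
- *70%/70%, same sensitivity in every patient, FP proportional to true events.* Given n, FP is Poisson(0.3n) and FN is binomial(n, 0.3). Variance = (0.30 + 0.21) × 192.8 = 98.3. Limits ±1.96 × √98.3 / 7 = ±2.8/h.
- *95%/95%, FP constant per hour.* Variance = 2 × 0.05 × 192.8 + (7 × 0.05)² × 680 = 102.6. Limits ±2.8/h.
- *70%/70%, FP constant per hour.* Variance = 2 × 0.30 × 192.8 + (7 × 0.30)² × 680 = 3,115. Limits ±15.6/h.
- *90% sensitivity, no FP.* Bias = −0.1 × 27.5 = −2.8/h. Variance = 0.10 × 192.8 + (7 × 0.10)² × 680 = 352.5. Limits ±5.3/h about the bias.
- *70% sensitivity, no FP.* Bias = −0.3 × 27.5 = −8.3/h. Variance = 0.30 × 192.8 + 2.1² × 680 = 3,057. Limits ±15.5/h about the bias.

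Simulation of 4,000,000 nights per case agrees with these to within 0.05/h. It also covers detectors whose performance varies between patients:

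| Sensitivity / PPV | Pattern of errors | Bias (/h) | Limits about the bias (/h) |
|---|---|---|---|
| 70% / 70% | FP proportional, same sensitivity in all | 0 | ±2.8 |
| 70% / 70% | sensitivity SD 0.10, FP coefficient of variation 0.3 | 0 | ±10.4 |
| 70% / 70% | sensitivity SD 0.15, FP coefficient of variation 0.5 | 0 | ±16.0 |
| 70% / 70% | FP constant per hour | 0 | ±15.6 |
| 95% / 95% | FP constant per hour | 0 | ±2.8 (slight slope) |
| 90% / 100% | no FP | −2.8 | ±5.3 |
| 70% / 100% | no FP | −8.3 | ±15.5 |

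The first and fifth rows give the same bias and limits for very different detectors. The sixth row, a better detector than the first, looks worse.

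**Type.** Take 150 obstructive and 50 central events, with error rates chosen to cancel: 20% of obstructive events are called central and 60% of central events are called obstructive.
- KCG obstructive total = 150 × 0.8 + 50 × 0.6 = 150. KCG central total = 150 × 0.2 + 50 × 0.4 = 50. Both match PSG.
- Central sensitivity = 20/50 = 40%. Central PPV = 20/50 = 40%.
- Observed agreement = (120 + 20)/200 = 0.70. Expected agreement = 0.75² + 0.25² = 0.625. Kappa = (0.70 − 0.625)/(1 − 0.625) = 0.20.

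Type-specific count plots would show perfect agreement for this night.

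**The case against.** The strongest reply is that the protocol does not call Bland-Altman the sole or primary analysis. It commits to type accuracy in the next sentence, and choosing the statistic is ordinary SAP work. The definitions, overlap rule and interval method can indeed go to a SAP. But the protocol has already named methods for this group, and they do not answer its own question; a SAP that follows them carries the mismatch forward.

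Other points, and what stands of each:
- *Sensitivity and accuracy are the hypothesis for the whole series, not a Group B endpoint.* True, but Group B sits under the main hypotheses, and accuracy by type is stated for it directly. Bland-Altman does suit part of the Group B aim, such as time in bed and nightly rate.
- *A qualitative comparison might mean comparing event categories.* The wording allows it, but it would still name no measure of accuracy.
- *The ±2.8/h case is contrived.* It is the best case for concealment, and the cancelling labels were chosen to cancel. With variation between patients, or constant false events, a 70% detector shows visibly poor limits, and one-way type errors would show in type-specific plots. The examples prove that the plots do not determine sensitivity, not that concealment is likely.
- *Sensitivity and PPV alone would still not match the quoted specificity and accuracy.* Fair. Those earlier figures came from selected periods of sleep and did not cover central apnoea, so they are a loose benchmark in any case.
- *Group D is not tied to the Bland-Altman result.* Correct: no criterion is stated. Group B must still be validated first.

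**Conclusion.** The concern holds and should be fixed. It is a mismatch between the stated method and the stated question, which can be read directly from Section 2 and depends on no assumed figure. The numbers show the size of the gap: under the assumed rates, bias 0 with limits of ±2.8/h fits both a detector with sensitivity and PPV of 70% and one with 95%, while a 70% detector can show limits anywhere from ±2.8 to ±16.0/h. Identical totals by type can coexist with a central sensitivity of 40% and kappa of 0.20. These figures rest on the assumed event-rate distribution, night length and error patterns, and on nightly counts or rates being what is plotted. The recorded data stay usable; it is the stated analysis that falls short.

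**What to change.** In the Group B text, make the primary comparison event by event:
- Match KCG events to PSG events by a stated time-overlap rule.
- Report sensitivity, PPV and false events per hour.
- Give a KCG-by-PSG cross-table of event type (obstructive, central, mixed, none), with sensitivity for each type.
- Use confidence intervals that allow for clustering of events within patients.
- If a figure comparable to the quoted specificity is wanted, add sensitivity and specificity by scoring epoch.
- State that KCG events are generated without sight of the PSG scoring, as Group A already does for the computer-generated sequence.
- Keep Bland-Altman for nightly event rate and time in bed, and name those as the plotted quantities.

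The cost is a sentence or two and some programming, plus the need to fix the overlap rule in advance. KCG and PSG are already recorded simultaneously, so no extra data or patient burden follows. Naming the accuracy measures also gives the Group B sample size, still to be calculated, something to be based on.

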breathing effort thereafter. We will test the hypothesis that these respiratory abnormalities are readily detectable by the KCG.

3. Methods

Study design and recruitment, expertise of the research group

Study A is an interventional pre-study on voluntary breath holding on healthy subjects. The parameter taken into consideration for sample size calculation in this group is the total (linear and rotational) systolic kinetic energy of the SCG (S_{sys_kin}) and the rolling ratio between the mean value and the standard deviation of this parameter: $H = \text{Mean}(S_{sys_kin}) / \text{Std}(S_{sys_kin})$. H discriminated voluntary obstructive apneas from episodes of normal respiration in a healthy volunteer ($H = 1.1627$ and 0.2308 , respectively). The sample size is determined according to: $2 \cdot (Z_{\alpha} + Z_{1-\beta})^2 \cdot \sigma^2 / \Delta^2$, where $\alpha = 5\%$ is the accepted error, leading to $Z_{\alpha} = 1.96$ (2-sided); $\beta = 95\%$ is the power of the study, leading to $Z_{1-\beta} = 1.64$; σ is the estimated standard deviation of H; Δ is the estimated effect of obstructive sleep apnea on H in patients. σ ($H_{baseline}$) = 0.1247 was obtained by H determinations on a group of healthy subjects who were breathing regularly. The difference in H during regular breathing and voluntary obstructive apnea, divided by 10 (because voluntary apneas may have induced larger changes than those experienced by patients) is $\Delta = (1.1627 - 0.2308) / 10 = 0.09319$. Thus, the estimated sample size for study A is 46.

Studies B and C are observational investigations on subjects referred for PSG as required by their medical condition and which fulfill the inclusion/exclusion criteria described previously. The number of subjects will be calculated accordingly to the results of the pre-study (group A).

Study D is an observational prospective investigation conducted on unselected consecutive patients without recruitment restrictions, in order to validate the KCG on the real population. Since we do not know how many patients will be necessary for the validation of our screening device, we speculate a size simple of 100 subjects.

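### Group D's stated conclusion about patients with co-morbidities is tied to the group as a whole, and an overall result in 100 consecutive referrals cannot support it

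*Protocol*

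**What the plan says.** Section 2 of the protocol (Aims and hypothesis tested, Main hypotheses) describes Group B as recruited from suspected sleep apnoea cases admitted for a sleep test, but "only in selected patients, who will not disclose marked abnormalities which could hamper the reliability of the KCG recordings". The list that follows covers valve disease, rhythm and conduction disorders, drugs that slow the heart, pacing, heart failure and movement disorders. Group C carries the same restriction, and Group A is healthy volunteers.

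Of Group D, section 2 says "we plan to extend the recordings on 100 unselected consecutive patients who will undergo PSG recordings because of complains of sleep apnoea", and adds: "This will validate the clinical usefulness of KCG recording for the detection of sleep apnoea even in patients with multiples co-morbidities".

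Section 3 (Methods, Study design and recruitment) describes the same group as "conducted on unselected consecutive patients without recruitment restrictions, in order to validate the KCG on the real population". It gives the basis for its size as: "Since we do not know how many patients will be necessary for the validation of our screening device, we speculate a size simple of 100".

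**The concern.** Group D serves two aims. One is to show how KCG performs in the referred population, and unselected consecutive sampling suits that aim. The other is to show that KCG still works in the patients set aside in Groups B and C. For that second aim, only Group D patients who have one of the excluded conditions carry information. A Group D patient who would have passed Group B's criteria repeats Group B's population.

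The protocol attaches the second conclusion to the group as a whole. It sets no stratum, no minimum number of patients with an excluded condition, and no separate result on which the conclusion depends. Its own reason for the exclusions is that performance may differ in these patients.

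The stake is high for this project. The background in section 1 and the Perspectives in section 4 argue for KCG partly on the ground that existing home tests are not recommended in patients with cardiovascular and other co-morbidities. If KCG fails in them and the overall figure does not show it, the claim fails where it matters most.

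**Working it through.** **No figure to reproduce.** The 100 in Group D is described as a speculation, with no effect size, precision or power behind it. The check therefore uses assumed values.

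**Who can enter which group**

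| Group | Source | Patients with a Group B exclusion |
|---|---|---|
| A | healthy volunteers | not studied |
| B | suspected apnoea, sleep unit | left out |
| C | diagnosed OSA, nCPAP | left out |
| D | consecutive PSG referrals | can enter, alongside Group-B-eligible patients |

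**Inputs (all assumed; the protocol gives none of them)**
- Sensitivity in Group-B-eligible patients: 90%.
- Sensitivity in patients with at least one Group B exclusion: 60%.
- f, the share of patients with apnoea who have an exclusion: 10% to 70%.
- One yes/no KCG result per patient against PSG.

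**Overall sensitivity** = 0.90 × (1 − f) + 0.60 × f = 0.90 − 0.30 × f

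| f | Overall | Drop below 90% | Excess over the 60% stratum |
|---|---|---|---|
| 10% | 87% | 3 points | 27 points |
| 20% | 84% | 6 | 24 |
| 30% | 81% | 9 | 21 |
| 40% | 78% | 12 | 18 |
| 50% | 75% | 15 | 15 |
| 60% | 72% | 18 | 12 |
| 70% | 69% | 21 | 9 |

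**How much of a drop would be noticed.** Suppose 70 of the 100 have apnoea and KCG detects 63 (90%). The exact (Clopper-Pearson) 95% interval is 80.5% to 95.9%. Overall values of 87%, 84% and 81% lie inside it; 78% does not. So a stratum at 60% can pass unseen mainly when f is about 30% or less. At half or more the drop is plain.

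**The same check with 95% and 60%.** Overall sensitivity is 91.5%, 88%, 84.5%, 77.5% and 70.5% at f = 10%, 20%, 30%, 50% and 70%. With 70 apnoea patients and f = 20% (56 eligible, 14 with an exclusion), the expected counts are about 53/56 and 8/14. The overall figure is 61/70 = 87% (exact 95% CI 77% to 94%). The stratum the claim is about gives 8/14 = 57% (29% to 82%).

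**What a separate report could show.** If 60% is observed in the stratum with an exclusion:

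| Detected / with apnoea | Exact 95% CI |
|---|---|
| 6/10 | 26% to 88% |
| 12/20 | 36% to 81% |
| 18/30 | 41% to 77% |
| 24/40 | 43% to 75% |

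**How many such patients to expect.** With 100 enrolled, the number with both apnoea and an exclusion is 100 × prevalence × f, taking f to be the same among all enrolled. At 50% prevalence and f = 10% that is 5. At 90% prevalence and f = 50% it is 45. Nothing in the protocol says where in this range the sample will fall.

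**The case against.** The strongest reply is that Group D is given only a sampling frame, a size and an aim. No estimator or success threshold is stated, and a breakdown by co-morbidity could sit in a statistical analysis plan not seen here. That stands as far as it goes: a missing subgroup table would not be a fault of the protocol. But the protocol does not leave the conclusion to a later document. It states it, and attaches it to the whole group.

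Several stronger readings are tempting and should not be made:
- **That the plan commits to one pooled analysis.** No section says so. What is fixed is one group, one size and one conclusion.
- **That a large part of Group D would have qualified for Group B.** No figure supports this. The exclusion list is broad, and the background says cardiovascular patients above all should now be evaluated, so the share with an exclusion could be high. The remark that recruitment should be easy rests on the device being unobtrusive and says nothing about eligibility.
- **That an overall result would always conceal failure.** It would not; the drop becomes visible as the share rises. With no threshold stated, it is also not shown that 78% or 87% would be declared a validation.
- **That uninterpretable recordings will be dropped.** Nothing in the protocol says this.

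Two limits also stand. Having at least one Group B exclusion is not the same as having several co-morbidities: a patient with respiratory and metabolic disease may have none of the listed conditions, while one taking only a listed drug has one. And the calculation assumes a yes/no result per patient, while Group B is to be analysed with agreement plots. A mean difference averages over strata in the same way, but the figures above apply only to sensitivity.

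**Conclusion.** The point holds as a mismatch between a stated conclusion and the group it is drawn from. Group D can support a statement about the patients referred to this sleep unit. Its overall result cannot by itself support the statement that KCG works even in those with co-morbidities that may hamper the signal.

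The size depends on an unknown share. Under the assumed 90% and 60%, overall sensitivity runs from 87% at a 10% share to 69% at a 70% share, and concealment is a practical risk mainly at about 30% or less. At larger shares the overall figure would reveal a problem but still not locate it. The change is worth making because it alters what Group D can conclude and uses criteria the protocol already contains.

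**What to change.** - Keep unselected consecutive sampling in Group D.
- At enrolment, classify each Group D patient by Group B's existing exclusion list.
- Report KCG-versus-PSG accuracy, with confidence intervals, separately for patients with and without an exclusion.
- Base any claim about patients with KCG-hampering co-morbidities on the stratum with an exclusion. Word it in those terms rather than as multiple co-morbidities in general.
- Limit the overall result to a claim about the referred population.
- State in advance that the co-morbidity claim will not be made if that stratum is too small for a useful interval; 6/10, with 26% to 88%, is an example of one that is not useful.

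The cost is one baseline classification and a stratified report, with no extra patients or procedures. The downside is that the co-morbidity conclusion rests on fewer than 100 patients, has a wider interval, and may turn out not to be possible.

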Complete laboratory polysomnography (PSG) is the gold standard to diagnose SDB (50, 51). However, it is an expensive, time-consuming and uncomfortable tool, limiting its wide-spread use despite the high frequency of SDB in the general population. However, considering the high prevalence of SDB in the general population and the change in the profile of patients at risk of SDB and then, who should be evaluated for, there is growing interest in the research of alternative strategies to reach the most of patients at possible. A number of home sleep testing devices has been proposed over years to screen patient at risk of SDB, but according to the guidelines, they are NOT recommended for patients with cardiovascular comorbidities (50). Moreover, the devices available nowadays do not provide any information on the direct impact of the apnoea on the cardiovascular system.

Nevertheless, taking into account the high prevalence of SDB and the limited accessibility of expensive sleep testing *on one side* and, *on the other side*, the marked recent technological advances in SCG and BCG technologies *as well as* the peculiar hemodynamic characteristics of sleep apnoea episodes, we wish to test

the hypothesis that modern SCG and BCG recordings can provide an highly accurate assessment of sleep apnoea, and evaluate the effects of nCPAP therapy.

There are several reasons to believe that the implementation of recent improvements in SCG-BCG will allow a precise quantification of such sleep-related events:

- 1) The cyclic pharynx collapses during sleep are associated to brain arousal, intrathoracic pressure swings (the so called ‘Mueller – manoeuvres’), and intermittent episodes of hypoxaemia and re-oxygenation (45). When respiration resumes, the cardiac output faces a markedly increased peripheral sympathetic activity, leading to sudden rises in systemic blood pressure, and reflex reductions in heart rate, while the opposite occurs during the periods of respiratory collapse. As explained above, these changes are likely to induce marked modifications in the amplitude and temporal recording assessed by SCG recordings, as well as in the “I”, “J” and “K” waves obtained from the BCG.

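### Does the R-J interval hypothesis contradict the protocol's own account of blood pressure during apnoea and at resumption of breathing?

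*Protocol*

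**What the plan says.** Two places in the protocol bear on this point.

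The first is the list of secondary hypotheses in section 2 (Aims and hypothesis tested). It introduces the parameter with "We will also asses the R-J interval which is related to blood pressure" and says the investigators will "determine if this parameter rises during the apneas and arousals when sympathetic activity is increased". Apnoeas and arousals are named together, with one direction and one reference to sympathetic activity. The sign of the relation between R-J and blood pressure is not given.

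The second is the background section on sleep-disordered breathing and kino-cardiography, point 1 of the reasons for expecting the method to work. It describes the haemodynamics of an event in two phases. On the return of breathing it says: "When respiration resumes, the cardiac output faces a markedly increased peripheral sympathetic activity". It gives an abrupt increase in blood pressure and a reflex slowing of the heart as the result at that moment. On collapse it then adds: "while the opposite occurs during the periods of respiratory collapse". The next sentence turns this into a reason to expect signal changes: "these changes are likely to induce marked modifications in the amplitude and temporal recording assessed by SCG recordings", and likewise in the BCG I, J and K waves.

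**The concern.** The background gives blood pressure one direction during collapse and the other at resumption. The secondary hypothesis takes a parameter whose main stated property is a link to blood pressure and looks for the same direction in both phases. The background passage is also the protocol's own argument for why these signals should respond to apnoea, so it cannot be set aside as general introduction.

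Two consequences seemed possible. First, a fall in R-J in one phase would count against the hypothesis as worded, although the background could be read as giving reason to expect it. Second, if R-J were averaged over apnoea and arousal together, opposite changes would partly cancel and a real effect could be missed.

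The sympathetic clause raises a similar question. If it restricts the hypothesis to periods of raised sympathetic activity, it fits resumption well, but it is less clear which part of the apnoea it covers.

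**Working it through.** No figure in the protocol is attached to R-J, so the check is a comparison of the two texts.

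| Phase | Blood pressure (background, point 1) | Heart rate (background, point 1) | Sympathetic activity (background, point 1) | R-J (secondary hypotheses) |
|---|---|---|---|---|
| Respiratory collapse | opposite of resumption | opposite of resumption | not clearly stated | asks whether it rises |
| Resumption (taken here as the arousal phase) | sudden rise | reflex fall | markedly increased | asks whether it rises |

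**Step 1: blood pressure.** Suppose R-J depended on blood pressure alone and monotonically. Since blood pressure moves in opposite directions in the two phases, R-J would do so too, whichever sign the relation has. Under that supposition R-J could not rise in both phases, so the tension is real.

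**Step 2: does the protocol make that supposition?** It does not. It says only that R-J is related to blood pressure. The same part of section 2 names other influences on cardiac timing: preload, afterload and sympathetic effects on contractility for PEP and LVET, and intrathoracic pressure swings for IVRT in obstructive apnoea. It does not list them for R-J, but it does not exclude them either. R-J could rise in both phases for different reasons without contradicting the background.

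**Step 3: does the background predict a direction for R-J?** It does not. It expects marked modifications of the signals, gives no direction for them and does not mention R-J. The step from opposite blood pressure changes to opposite R-J changes is the reader's inference.

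**Step 4: sympathetic activity.** The background says that cardiac output meets raised sympathetic activity when breathing resumes. This allows for activity that is already high late in the apnoea. The clause about the opposite follows directly on blood pressure and heart rate and attaches most naturally to those two. The text does not clearly place low sympathetic activity in the apnoea, so there is no firm contradiction here.

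**Step 5: dilution.** Let the R-J changes from normal breathing be d₁ in apnoea and d₂ at resumption, with a share w of the analysed time in apnoea. A pooled change would be w·d₁ + (1 − w)·d₂, which shrinks towards zero when d₁ and d₂ have opposite signs. The protocol gives no value for d₁, d₂ or w, and it does not say that the phases are pooled. The size cannot be computed, and the mechanism is hypothetical.

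**Step 6: does anything in the design rest on R-J?** The only formal sample-size calculation is for Study A (section 3, Methods). It uses H, a ratio derived from the SCG kinetic energy, with σ = 0.1247 and Δ = (1.1627 − 0.2308)/10 = 0.09319:

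2 × (1.96 + 1.64)² × 0.1247² / 0.09319² = 25.92 × 0.015550 / 0.0086844 = 46.4, against 46 stated.

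No R-J term enters. Study D's 100 subjects are described as speculative, and the numbers for Studies B and C are to be set from the results of Group A.

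**Step 7: can the phases be separated with the planned data?** Yes. Group A records "beat to beat non-invasive blood pressure (Finometer" together with the ECG while a computer program generates the breathing periods. In Groups B to D the PSG can label apnoeas and arousals. Arousals from sleep can be studied only in Groups B to D, because Group A performs voluntary manoeuvres.

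**The case for a change.** The strongest case for a change is this. The sentence stands under a hypotheses heading and names a single direction. Blood pressure is the one haemodynamic property it gives for R-J, apart from the sympathetic clause. The background on which the signals are justified has blood pressure moving in opposite directions, and no other section reconciles the two. The account of chronic mechanisms earlier in the background mentions sympathetic activation from intermittent hypoxaemia, but as a long-term effect, so it does not settle the timing within an event. A statistical analysis plan built on the sentence would inherit the ambiguity, and a wording change would need no new measurement.

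Much of this stands. The quotations are accurate, the wording is loose, and the blood pressure rationale does not by itself support a common direction. What does not stand is the step from loose wording to a defect in the plan. A question that the data may answer with no for one phase is an ordinary hypothesis. How the phases are delimited, separated or combined for a secondary parameter is commonly settled in the statistical analysis plan, which is not at hand. Prescribing two-sided comparisons by phase, preceded by a description in Group A of how R-J relates to blood pressure, would be an analysis preference and would go beyond correcting an error.

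**Conclusion.** No change to the plan is needed. The two places are not well aligned, but they do not contradict each other: one asks whether R-J rises, and the other describes blood pressure and heart rate without giving R-J a direction. A team following the text would measure R-J in apnoeas and in arousals and report the direction seen. If R-J moved differently in the two phases, that would be a finding of the study, and no wrong result follows from the wording.

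The reach is one exploratory secondary parameter. The main accuracy aims and the sample size of 46 do not depend on it, and no R-J magnitude can be derived from the protocol. The conclusion assumes that analysts keep apnoea and arousal apart, which the sentence's own naming of the two makes the natural course and which the planned recordings allow. If the phases were in fact pooled, dilution would become a fair concern, but nothing in the protocol says that they will be. Anyone editing the protocol for other reasons could align the two sentences, but this is editorial and optional.
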